10.0 Data Monitoring Plan

This is a single arm phase II study in patients with MDS who have failed therapy with or are intolerant of hypomethylating agents.

Primary objective: complete response (CR); overall survival.

Secondary objective: duration of response; relapse-free survival; safety.

It will be postulated that the treatment can achieve a CR rate of 20% and a median overall survival time of 6 months.

A maximum of 80 patient will be accrued at a rate of 2 to 5 patients per month (maximum accrual period 3.33 yrs). The CR, overall survival and toxicity will be monitored during the study, and all data will be used to update the prior distributions for toxicity and efficacy parameters. The study will be stopped for toxicity and futility based on the following stopping rules.

Efficacy monitoring

Complete response and overall survival will be monitored separately. The method of Thall, Simon, and Estey [9] will be used to monitor response and Bayesian time-to-event model [10] will be used to monitor overall survival.

a. CR

CR will be monitored in all pts using the method of Thall et al.[9] Denote the probability of CR by PE. We assume $PE \sim \text{beta}(0.4, 1.6)$. We will stop the trial if at any point that there is < 1% chance that the CR rate is > 20%. Stopping boundaries corresponding to this stopping rule and operating characteristics are listed in tables 1a and 1b. CR in the 4 months after the treatment will be included in the primary analysis.

Table 1a. Stop accrual if the number of response is equal to or less than indicated (i.e., # response) among number of patients accrued (i.e., # Patients). (PL=0.01)

# CR	0	1	2	3	4	5	6	7	8
# Pts	15	24	33	41	49	56	64	71	78

Table 1b: Operating characteristics of response (based on 10000 simulations) (PL=0.01)

True Probability	Stop Probability	Trial Sample Size Percentile		
		25%	50%	75%
0.05	0.992	15	24	33
0.1	0.735	24	41	80
0.15	0.301	64	80	80
0.2	0.086	80	80	80

b. Overall survival

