Bayesian time-to-event model will be used to monitor the overall survival [10]. Let T_e and T_s represent the overall survival time for the study and the historical treatment, respectively. We assume $T_e|Me$ and $T_s|Ms$ follow an exponential distribution with median Me and Ms , respectively. We further assume that the prior for Ms follows Inverse Gamma (IG) (35, 204) to reflect our knowledge of overall survival from the historical data, which has a mean of 6 months and a variance of 1.09. The prior for Me is assumed to be IG (3,12), which has the same mean as Ms but with a much larger variance (36) to reflect much greater uncertainty about the median time to progression of the study treatment.

The study will be monitored after the first 14 pts have been enrolled and then be repeated every month. The study will be stopped early if, based on the available data, we have little reason to believe that the median OS is 6 months or more. Formally, we'll stop the study early if there is < 5% chance that the median OS is 6 months or more. The operating characteristics of this decision rule are shown in the following table:

Table 2: Operating characteristics of Efficacy Monitoring(PL=0.05)

True Median OS (Mos)	P(Stop)	Mean Number of Pts (25%, 75%)
2	1	18 (15,20)
4	0.835	42 (21,63)
6	0.079	76 (80,80)
7	0.024	79 (80,80)

Toxicity Monitoring

Toxicity will be monitored in all pts using the method of Thall et al 1995 [9]. Toxicity is defined as non-hematologic grade 3 or 4 toxicities during the treatment course. Denote the probability of toxicity by E, where study drug related toxicity is defined as any Grade 3 or greater non-hematological toxicities. We assume $E \sim \text{beta}(0.6, 1.4)$. We will stop the trail if at any point $\Pr(E > 0.30 | \text{data}) > 0.95$, i.e. if at any time during the study, we determine that there is > 95% chance that the study drug related toxicity rate is > 30%. Toxicity monitoring will be done in cohorts and the trial will be stopped if (number of toxicity observed / among number of patients) $\geq 6/10, 8/15, 10/20, 12/25, 14/30, 16/35, 18/40, 19/45, 21/50, 23/55, 25/60, 26/65, 28/70, 30/75, \text{ and } 31/80$.

Table 3: The operating characteristics for toxicity monitoring are summarized in the following table

True toxicity probability	Probability of early stop	Sample size percentiles (10, 25, 50, 75, 90)
0.1	0	80 80 80 80 80
0.2	0.012	80 80 80 80 80
0.3	0.188	23 80 80 80 80
0.4	0.755	10 15 36 79 80
0.5	0.99	10 10 15 25 41

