Early termination of the study can be caused by either lack of efficacy or too much toxicity. If the efficacy and toxicity are considered jointly, the stopping probabilities will be higher than the probabilities shown in Tables 1 to 3.

Table 4 shows several scenarios of the joint stopping probabilities assuming that efficacy and toxicity are independent.

Table 4: Operating characteristics considering efficacy and toxicity jointly

True probability of CR	True Median OS (mos)	True Probability of Toxicity	Early Stop Probability
0.25	7	0.2	0.06
0.25	4	0.2	0.84
0.25	7	0.5	0.99
0.2	6	0.3	0.316
0.1	4	0.4	0.989
0.1	6	0.2	0.759
0.1	7	0.4	0.937

All calculations were performed using OnearmTTE and Multc99.

Trial Conduct

The Department of Biostatistics will provide and maintain a website ("Clinical Trial Conduct") for monitoring of the overall survival. The Clinical Trial Conduct website resides on a secure server, and access is gained through usernames and passwords provided to personnel responsible for enrolling patients and updating patient data. The website is accessed through a browser using secure socket layer (SSL) technology.

Personnel responsible for enrolling patients on trials will be trained in the use of the trial website, with emphasis on the importance of timely updating of follow-up times and recording of events. The monitoring rules for the overall survival will be automatically evaluated each time patient data are updated on the trial website. If the stopping rule is met, the study statistician, research nurse, and principal investigator will each receive an email notification that the stopping boundary has been met.

Analysis Plan

For discrete or categorical data, descriptive statistics will include tabulations of frequencies. For continuous data, summary statistics including n, mean, standard deviation, median, minimum and maximum will be computed. The posterior CR rate and its 95% credible intervals will be estimated. The Kaplan-Meier method will be used to estimate the probability of the overall survival.

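### The overall-survival stopping rule has two evaluation schedules, Table 2 describes only the monthly one, and the plan does not say which evaluations bind

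*Combined protocol and SAP*

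**What the plan says.** Section 10.0, part b (Overall survival), fixes the timing: "The study will be monitored after the first 14 pts have been enrolled and then be repeated every month". The action limit follows: "we'll stop the study early if there is < 5% chance that the median OS is 6 months or more". Table 2 is introduced as the operating characteristics of that decision rule. It gives stopping probabilities of 0.835, 0.079 and 0.024 at true medians of 4, 6 and 7 months.

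The Trial Conduct text later in Section 10.0 describes the monitoring website: "The monitoring rules for the overall survival will be automatically evaluated each time patient data are updated on the trial website". It continues: "If the stopping rule is met, the study statistician, research nurse, and principal investigator will each receive an email notification" that the boundary has been met. This text repeats neither the monthly interval nor the 14-patient start, and it does not withdraw either. It gives no interval for updates, only an emphasis on timely entry of follow-up and events. No operating characteristics are given for update-driven looks.

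**The concern.** Each extra look at an unchanged 5% cut-off is another chance to cross the boundary by bad luck. OS is a primary objective, and this rule can close accrual on a treatment that meets its 6-month target. If update-driven crossings count, the false-stop rates in Table 2, and the joint rates in Table 4 built from them, belong to a different procedure from the one being run. There is also a practical gap. A team that receives the email midway between monthly looks, or before the 14th patient, cannot tell from the plan whether the trial has stopped.

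**Working it through.** **Inputs, all from Section 10.0.** Survival times "follow an exponential distribution with median Me and Ms , respectively". The prior for the study median Me is IG(3, 12) and for the historical median Ms is IG(35, 204). The cut-off is 0.05. On size and pace: "A maximum of 80 patient will be accrued at a rate of 2 to 5 patients per month".

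**Prior check.** IG(35, 204): mean 204/34 = 6, variance 6²/33 = 1.09. IG(3, 12): mean 12/2 = 6, variance 6²/1 = 36. Both agree with the plan.

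**Rule simulated.** With d deaths and total follow-up time T, the posterior for Me is IG(3 + d, 12 + ln2 × T). Stop if Pr(Me > Ms | data) < 0.05. Writing b = 12 + ln2 × T, Me > Ms exactly when G1/G2 < b/204, with G1 ~ Gamma(3 + d) and G2 ~ Gamma(35), so the boundary comes from the 5% quantile of Beta(3 + d, 35). The comparison with Ms is used because it reproduces Table 2. The literal fixed 6-month wording does not: it gives 0.19-0.25 at a true 6-month median with monthly looks. That is a separate matter and no part of the size given here.

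**Assumptions.** Poisson accrual, a maximum of 80 patients, looks continuing for 6 months after the last enrolment, up-to-date follow-up at every look, and the 14-patient start kept. There were 10,000 trials per cell, so the Monte Carlo standard error at 0.09 is √(0.09 × 0.91/10,000) ≈ 0.003.

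| True median (stated) | Accrual per month | Monthly, first look at patient 14 | Monthly, first look a month later | Every enrolment | Every death |
|---|---|---|---|---|---|
| 6 months (0.079) | 2 | 0.087 | 0.080 | 0.093 | 0.111 |
| | 3 | 0.089 | 0.081 | 0.100 | 0.122 |
| | 4 | 0.088 | 0.081 | 0.108 | 0.128 |
| | 5 | 0.086 | 0.079 | 0.110 | 0.131 |
| 7 months (0.024) | 2 | 0.031 | 0.027 | 0.035 | 0.042 |
| | 3 | 0.034 | 0.029 | 0.038 | 0.050 |
| | 4 | 0.035 | 0.030 | 0.043 | 0.054 |
| | 5 | 0.034 | 0.029 | 0.046 | 0.056 |
| 4 months (0.835) | 2 | 0.853 | 0.851 | 0.857 | 0.876 |
| | 3 | 0.852 | 0.849 | 0.858 | 0.881 |
| | 4 | 0.834 | 0.832 | 0.842 | 0.868 |
| | 5 | 0.820 | 0.819 | 0.837 | 0.864 |

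**Reproduction.** The monthly columns lie within 2 points of Table 2 at all three medians. Table 2 therefore describes monthly looks, and the effect of the schedule can be isolated.

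**Why more looks matter.** From patient 14 to patient 80 takes (80 − 14)/3 = 22 months at 3 per month, so about 23 monthly looks. A look at each enrolment gives 80 − 14 + 1 = 67. At 5 per month the contrast is sharper: 66/5 = 13.2 months, about 14 looks against 67.

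**Other schedules, true median 6 months, looks during accrual only.** Monthly 0.088-0.094, weekly 0.105-0.120, each death 0.111-0.119. Updates every two months give 0.066-0.073, below the monthly figure.

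**Carry-through to Table 4.** The row with CR 0.2, OS 6 months and toxicity 0.3 is 1 − (1 − 0.086)(1 − 0.079)(1 − 0.188) = 1 − 0.914 × 0.921 × 0.812 = 0.316, as printed. Replacing 0.079 by 0.10 gives 1 − 0.914 × 0.90 × 0.812 = 0.332, and by 0.12 gives 1 − 0.914 × 0.88 × 0.812 = 0.347.

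**The case against.** The strongest reply is that the two texts are compatible. Trial Conduct refers to the monitoring rules already defined, which include the 14-patient start, and the only consequence it names is an email. Software may check continuously while part b fixes the formal looks. On that reading Table 2 stands unchanged. It is a natural reading, but the plan does not state it, and an email saying the stopping boundary has been met invites action. The need for clarification stands.

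Three stronger inferences are not supported:

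- **That the website drops the 14-patient start.** False stopping would then be about 0.14 at 6 months and 0.06 at 7 months. But Trial Conduct is only silent on the start, and silence is not a waiver.
- **That the Table 2 figures are simply wrong for the trial as run.** They fail only if every evaluation binds and updates come more often than monthly. Updates every two months or less often would not raise false stopping.
- **That uneven data entry makes matters much worse.** If deaths are entered at once while survivors' follow-up is refreshed only monthly, the 6-month figure reaches 0.16-0.30. The plan asks for timely updating of both, so this cannot be attributed to it.

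It is also fair to say that extra looks help when the treatment is poor. At a true median of 4 months, looking at every death raises stopping by 2.3 points at 2 per month (0.853 to 0.876) and by 4.4 at 5 per month (0.820 to 0.864). Across all settings tried, the gain is about 2 to 6 points.

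**Conclusion.** The inconsistency is real: one stopping rule has two evaluation schedules in the current text, with no statement of which evaluations bind. Its numerical effect is conditional and modest. If update-driven evaluations bind, come more often than monthly and respect the 14-patient start, false stopping rises like for like from about 0.08-0.09 to about 0.10-0.12 at a true 6-month median, and from about 0.02-0.035 to about 0.035-0.05 at 7 months. The typical rise at 6 months is 1 to 3 points. The largest is 4.5 points (0.086 to 0.131), at 5 patients per month with a look at every death and looks continuing after accrual. The update frequency is the main assumption. The plan gives no interval, but 2 to 5 enrolments a month plus deaths make more-than-monthly updates likely. The point deserves correction because the remedy is small and makes the stated error rates apply to the rule actually run. It does not show that the trial's futility design is unsound.

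**What to change.** Reconcile part b and Trial Conduct in one sentence: the binding OS evaluations are the monthly ones starting after 14 patients are enrolled, and website alerts at other times are informational. Set the website notice to match. The cost is that a true futility signal may be acted on up to a month later, and the small gain in correct stopping at a 4-month median is given up.

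If update-driven evaluation is meant to bind, say so, state whether the 14-patient start applies and how often updates are expected, and rerun Table 2 and the Table 4 rows built on it for that schedule. That costs a rerun of the simulations and acceptance of the higher false-stop rates, or a recalibrated cut-off.

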11.0 Reporting Requirements

Please refer to Appendix D (Leukemia-specific adverse event recording guidelines) and Appendix E (Expected adverse events in leukemia).

Serious Adverse Event Reporting (SAE)

A serious adverse event is – any adverse drug experience occurring at any dose that results in any of the following outcomes:

- Death
- A life-threatening adverse drug experience – any adverse experience that places the patient, in the view of the initial reporter, at immediate risk of death from the adverse experience as it occurred. It does not include an adverse experience that, had it occurred in a more severe form, might have caused death.
- Inpatient hospitalization or prolongation of existing hospitalization
- A persistent or significant disability/incapacity – a substantial disruption of a person's ability to conduct normal life functions.
- A congenital anomaly/birth defect.

Important medical events that may not result in death, be life-threatening, or require hospitalization may be considered a serious adverse drug experience when, based upon appropriate medical judgment, they may jeopardize the patient or subject and may require medical or surgical intervention to prevent one of the outcomes listed in this definition. Examples of such medical events include allergic bronchospasm requiring intensive treatment in an emergency room or at home, blood dyscrasias or convulsions that do not result in inpatient hospitalization, or the development of drug dependency or drug abuse (21 CFR 312.32).

- All events occurring during the conduct of a protocol and meeting the definition of a SAE must be reported to the IRB in accordance with the timeframes and procedures outlined in "University of Texas M. D. Anderson Cancer Center Institutional Review Board Policy on Reporting Serious Adverse Events".

· Serious adverse events will be captured from the time the patient signs consent until 30 days after the last dose of drug. Serious adverse events must be followed until clinical recovery is complete and laboratory test have returned to baseline, progression of the event has stabilized, or there has been acceptable resolution of the event.

Recommended Adverse Event Recording (PDMS) Guidelines

Attribution	Grade 1	Grade 2	Grade 3	Grade 4	Grade 5
Unrelated	Phase I	Phase I	Phase I Phase II	Phase I Phase II Phase III	Phase I Phase II Phase III
Unlikely	Phase I	Phase I	Phase I Phase II	Phase I Phase II Phase III	Phase I Phase II Phase III
Possible	Phase I Phase II	Phase I Phase II Phase III			
Probable	Phase I Phase II	Phase I Phase II Phase III			
Definitive	Phase I Phase II	Phase I Phase II Phase III			

